## **List of Abbreviations**

- EEG Electroencephalogram
- ECG Electrocardiogram
- **GCP** Good Clinical Practices
- ICH International Council Harmonization
- IRB Institutional Review Board
- COI Conflict of Interest
- Q&A Question and Answer
- PST Pacific Standard Time
- HRV Heart Rate Variability
- RCH Remote Coherence Healing

# 1 Background/ Significance

This submission of MED02 is an extension of the currently approved protocol MED01 #1273003. Under this new protocol, we want to expand explorative data collection to cover two new areas of interest. One area is to collect pilot data on coherence healing (outlined in experiment A). Under this paradigm, meditators (Healers) utilize meditation to facilitate healing of a person (Healee).

The second area expands pilot data collection to [name] meditation community, independent from specific meditation events (outline in experiment C). Lastly, this new protocol builds upon the ability of collecting data during an event (outlined in experiment B).

Meditation has been used by cultures across the globe for millennia. In Eastern religions, meditation is common and has its roots in Hindu and Buddhist traditions and manuscripts dating back hundreds of years after Buddha's death. Additionally, effects similar to meditation have also been described in Muslim^2 and Christian prayers, as well as spiritual reflection and chanting, suggesting that these practices are an integral part of human culture and existence. In recent years, meditation as a therapeutic option and lifestyle choice has become increasingly popular in Western cultures. A paradigm shift is emerging in evaluating the relationship between spirituality and medicine. This shift is reflected by the increase in medical publications in the PubMed database containing the search term 'meditation'. Until the year 1970, below 2.2 manuscripts per year were published that contained this term. This average number increased by two orders of magnitude in recent years with an average of 26.4 between 1971 and 2000 and 244.6 from 2001 until present. Our specific interest is to establish and describe the molecular relationship between mind and body.

Current manuscripts investigate several effects of meditation on human biology and pathology. Specifically, there is an emphasis on stress reduction and utilization of meditation as an adjunct treatment in chronic pain and neuropsychiatric diseases such as anxiety and depression, sleep disorder, and post-traumatic stress disorder. For example, the following molecular and physiological effects of meditation are described. In a study investigating inflammatory biomarkers in inflammatory bowel disease, psychological and physical symptoms as well as C-reactive protein were significantly reduced in a group that participated in a Breath-Body-Mind Workshop. Another study investigated telomere biology in attendees of a 1-month long meditation event and concluded that training in an event setting may have effects on telomere regulation. Cortisol is a biomarker that has been shown to be positively influenced in subjects practicing mindfulness. Furthermore, influences of meditation on the heart-brain connection and the epigenetic clock have also been described.

Several studies have investigated brain waves measured with electroencephalography (EEG) in meditators and have looked at different meditation techniques. In one study investigating Vipassanna meditators, differences in brain wave recordings were found between novice, experienced senior and teacher meditators. In Brahma Kumaris Raja yoga meditators it has been shown that experienced meditators can shift reliably and consciously between rest and meditation with enhanced theta power (4-8Hz). Furthermore, an increased brain network integration and long-lasting changes in hippocampal functional topology during resting states have been described and associated with meditation.

Popularity of Complementary and Alternative Medicine (CAM) such as Yoga, Tai Chi, Qi Gon, and meditation has been rapidly increased and many patients in all the world use spiritual healing and other CAM practices. Spiritual actions and spirituality are intrinsic identities of humanity and potential healing forces.

Given this wide variety of studies and techniques and the positive effects of meditation and mindfulness practices, well-controlled studies are difficult to perform in everyday settings. Furthermore, studies aiming to phenotype the meditative state and integrating read-outs evaluating behavior, physiology, and molecular biology are currently not available. Studies examining specific known end points have been conducted but introduce bias and are ultimately limited in their scope. Limited investigations have approached the mind:body:molecular connection in an unbiased manner to identify novel and unique markers.Studying a community using the same meditation principles and practice will allow to control for a lot of the above mentioned difficulties in studying meditation. In addition, nan event setting here poses the unique situation that matching/controlling for several parameters such as housing, diet, climate, circadian pattern, and daily routine is possible additionally to matching in parameters such as gender, age, and body mass index. This provides a rare opportunity for a very well-controlled pilot study to explore and ultimately phenotype meditative state in the human organism.

# 2 Objectives

The objective of this study is to describe the effects of meditation on human well-being and function and to learn in greater detail what effect meditation has on the human organism. We are proposing experiments exploring three areas of interest (experiments A, B, C) utilizing procedures, including bio-psychosocial readouts, physiologic, and biologic/molecular measurements. We therefore propose a combination of different experimental components, as follows:

Experiment A: Measuring the effects of meditation on the Healer and Healee. Healers include members of [name] mediation community who participate in a healing event. Healees may include individuals who volunteer to receive a healing and may or may not be members of the [name] meditation community

Experiment B: Measuring the effects of meditation on the human organism. Here, we are interested in collecting data before, during, and after a meditation event (intervention) held by [name]. We will compare [name] meditators to controls and to meditators following other forms of meditation, including but not limited to mindfulness-based techniques, relaxation response, breath-based techniques, and prayer.

Experiment C: Measuring the effects of meditation within the meditation community. Here we are interested in collecting data from members of [name] meditation community on human well-being and function.

Particularly, we are interested in collecting the following data:

- 1. Questionnaire data (i.e. demographics, medical history, PROMIS measures)
- 2. Physiological readouts (i.e heart rate variability {HRV}, Electroencephalogram {EEG} and physiological readouts from wearables like FitBit, Garmin or Apple Watch)
- 3. Biological data (i.e blood, plasma, serum, and saliva)
- 4. FLIP Video Capture (record a 1.5-3 min video at the end of each day of the meditation retreat reflecting on their experiences)

We are hoping to contribute significantly to the understanding of the effects of meditation on human well-being and function and to establish a meditation whole-organism phenotype.

We propose the following aims:

Aim 1: Explore effects of meditation on Healer, Healee and their interactions.

Aim 2: Evaluate and/or correlate brain waves (EEG) and physiological readouts (HRV, wearable data) of meditating subjects with their experience in meditation techniques including novice (less than 6 months experience) and experienced meditators (more than 6 months experience).

Aim 3: Explore potential effects of meditation on molecular biology (e.g. biomarker and -omic changes) between novice and experienced meditators and controls.

Aim 4: Explore correlation between EEG state, HRV, wearable readouts, and molecular findings.

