## 4.2 Experiment B (Measuring the effects of meditation on the human organism)

#### 4.2.1 Inclusion Criteria

Potential subjects must meet all inclusion criteria:

- 1. Subjects must be 18 years of age or older.
- 2. Subjects must be a participant in a [name] meditation event.
- 3. Subject or an assigned representative must be willing and able to read and provide Informed Consent in English language.

Potential controls must meet all inclusion criteria:

- 1. Controls must be 18 years of age or older.
- 2. Controls must be willing and able to read and provide Informed Consent in English language.

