#### 4.2.2 Exclusion Criteria

Potential subjects must not meet any exclusion criteria:

- 1. Neurological diagnosis that could interfere/alter with EEG recordings such as epilepsy.
- 2. Subjects who had a heart transplant.
- 3. Subjects who have cardiac disease that could interfere with ECG recording such as but not limited to cardiac arrhythmia or disorder of cardiac conduction.
- 4. Subjects who have been diagnosed with a malignant disease that could interfere with blood parameters.
- 5. Subjects with any medical condition that by discretion of the Principal Investigator would be disqualified.

Potential controls must not meet any exclusion criteria:

- 1. Neurological Diagnosis that could interfere/alter with EEG recordings such as epilepsy.
- 2. Controls who had a heart transplant.
- 3. Controls who have cardiac disease that could interfere with ECG recording such as but not limited to cardiac arrhythmia or disorder of cardiac conduction.
- 4. Controls who have been diagnosed with a malignant disease that could interfere with blood parameters.
- 5. Controls with any medical condition that by discretion of the Principal Investigator would be disqualified.
- 6. Controls must not be a participant in a [name] meditation event.

**4.3 Experiment C** (Measuring the effects of meditation within the meditation community)

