## **5 Subject Recruitment**

Subject outreach will utilize [name] online presence (website, social media, etc.). Subjects will be recruited through prescreening emails to members of [name] meditation community and/or registered event participants. These emails will briefly explain the research study and offer the subject the option to follow a link for pre-screening.

For pre-screening, potential subjects will visit a pre-screening questionnaire via a HIPAA compliant software (ie. SurveyMonkey) and be asked general pre-screening questions based on

the inclusion and exclusion criteria. The questionnaire will also collect basic data such as demographics and past medical history.

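### Experiment B promises a comparison with meditators of other forms but provides no such group, and its control rules leave meditation practice unclassified

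*Protocol*

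**What the plan says.** Section 2 (Objectives) sets the comparison for Experiment B without condition: "We will compare [name] meditators to controls and to meditators following other forms of meditation". It lists the other forms as "including but not limited to mindfulness-based techniques, relaxation response, breath-based techniques, and prayer".

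Aim 2 in the same section divides meditating subjects into "novice (less than 6 months experience) and experienced meditators (more than 6 months experience". Aim 3 looks at molecular changes "between novice and experienced meditators and controls".

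The operative sections name two groups:

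- **Subjects.** Section 4.2.1: "Subjects must be a participant in a [name] meditation event". Section 5: "Subject outreach will utilize [name] online presence (website, social media, etc", and "Subjects will be recruited through prescreening emails to members of [name] meditation community and/or registered event participants". Section 6.3.2 then qualifies members of the community who pass pre-screening and anticipates 10 to 100 subjects, depending on the event.
- **Controls.** Section 4.2.1 asks for age 18 or over and consent in English. Section 4.2.2 adds health exclusions and one rule on exposure: "Controls must not be a participant in a [name] meditation event". Section 6.3.2 takes controls from event volunteers and from the family and friends of attendees, matches them on age and sex, and anticipates 5 to 20.

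**The concern.** An objective names a comparison group that the design does not supply. An analysis plan cannot repair this, because a cohort that is never made eligible, approached or counted cannot be created at analysis. A reader of the protocol would expect a result against mindfulness, breath-based or prayer practitioners that the study cannot produce.

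The second issue follows from the same gap. The study is about meditation, yet control status is defined by attendance at an event and not by practice. A volunteer or spouse with years of practice meets every stated control rule, although the six-month cut would class the same person as experienced. In a contrast of groups at one time point, a small or absent difference could then mean either that experience has no effect or that some controls also meditate. The study is an exploratory pilot, so what is at stake is interpretation and not a confirmatory test.

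**Working it through.** The protocol states no effect size, standard deviation, power or share of practising controls, so there is no figure to reproduce. The main check is a comparison of its sections.

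**1. Is there a place for the other-forms group?**

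- Eligibility (4.2.1, 4.2.2): criteria for subjects and for controls only.
- Recruitment (5): the organiser's online presence, community members and event registrants.
- Timeline (6.2.2): subjects and controls only.
- Selection and numbers (6.3.2): 10 to 100 subjects and 5 to 20 controls, with no third number.
- EEG audio (6.4.1): a recorded meditation for subjects, an audio book for controls, and no third condition.

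A practitioner of another form who attends the event might meet the subject criteria in Section 4.2.1. That person would then be exposed to the event, and Section 6.3.2 narrows subjects to community members. One who does not attend can enter only as a control, the group from which Section 2 distinguishes them.

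**2. Does any control rule concern practice?** The control criteria in Sections 4.2.1 and 4.2.2 and the matching in Section 6.3.2 cover age, consent, health, event participation and sex. The event rule does not reach practice at home or another form of meditation. The six-month cut is stated for meditating subjects and not for controls.

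**3. Which reading of Aim 3 is better supported?** Aim 3 speaks of biomarker and -omic changes. Section 2 describes the event as the intervention. Sections 6.2.2 and 6.3.2 take biological samples just before and just after the event, from both groups in Section 6.3.2. Section 6.6 describes its assays in pre/post terms. Together these favour change across the event. Aim 3 could loosely mean differences between groups, so a cross-sectional reading is not excluded.

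**4. Direction of effect on a cross-sectional contrast (illustration only).** Assume a share *p* of controls practises and each resembles experienced meditators to a degree *k*. The expected difference is the true one times (1 − *kp*):

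- *k* = 1: 1 − 0.2 = 0.80 for *p* = 0.2, and 1 − 0.4 = 0.60 for *p* = 0.4.
- *k* = 0.5: 1 − 0.1 = 0.90 and 1 − 0.2 = 0.80.
- *k* = 0: 1.00, which is close to the situation for change across the event.

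**5. Would restricting to non-practising controls be better?** It removes a bias of *kpD* (*D* = true difference in SD units) but cuts *n* controls to *n*(1 − *p*). Assuming a common SD, mean squared error falls only if (*kpD*)² > 1/[*n*(1 − *p*)] − 1/*n*. The number of meditators cancels, giving *D* > (1/*k*) × √{1/[*np*(1 − *p*)]}:

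- *n* = 20, *k* = 1: √(1/3.2) = 0.56 SD for *p* = 0.2, and √(1/4.8) = 0.46 SD for *p* = 0.4.
- *n* = 5, *k* = 1: √(1/0.8) = 1.12 SD and √(1/1.2) = 0.91 SD.
- *k* = 0.5 doubles each: 1.12 and 0.91 SD at *n* = 20, and 2.24 and 1.83 SD at *n* = 5.

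The control range in Section 6.3.2 is not stated to be a study total. If five events with 20 controls each were pooled (*n* = 100, an assumption), the threshold for *p* = 0.2 and *k* = 1 would be √(1/16) = 0.25 SD. Whether restriction helps therefore turns on quantities the document does not give.

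**The case against.** The missing group is hard to defend on the text, but its weight can be questioned. None of Aims 1 to 4 uses an other-forms group, no planned estimate is shown to depend on it, and deleting one clause resolves it. This stands, and it limits the seriousness without removing the inconsistency.

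On the controls the objection is stronger. If the event is the intervention, people not exposed to it are coherent controls, whether or not they meditate at home. Drawing them from people on site also has its own rationale in Section 6.1.2, which values shared diet, housing and sleep. Both arguments hold for change across the event.

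A reader might go further and infer any of three things. The documents do not support them:

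- **That Aim 3 is biased toward no difference.** This needs the cross-sectional reading, which is the less supported one, and a share of practising controls that is nowhere given.
- **That practising controls should be excluded.** With 5 to 20 controls, restriction lowers mean squared error only above 0.46 to 2.24 SD under the assumptions shown, so it may cost more than it gains.
- **That controls' practice goes unrecorded.** Section 5 gives only examples of the pre-screening content, and the questionnaires listed in Section 15 are not shown. They may already ask about it.

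**Conclusion.** The inconsistency holds with high confidence: the Experiment B objective states a comparison for which the protocol provides no eligible, recruited or numbered group and no EEG condition. It should be corrected before recruitment.

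The point about controls holds conditionally. Practising meditators can qualify as controls. That can weaken a baseline or cross-sectional contrast, and it matters much less for change across the event. No size of bias can be derived from the document. The factors of 0.60 to 1.00 above show direction under assumed values of *p* and *k* and are not estimates. The harm is to the interpretation of a pilot.

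**What to change.** 1. Delete the other-forms comparison from the Experiment B objective. Alternatively, define those people as a separate labelled cohort, with an eligibility criterion, a source, a number and an EEG audio condition, and do not count them as controls.
2. State that Aim 3 contrasts change across the event, or say explicitly that another contrast is meant.
3. Record the type and months of meditation practice of every control at pre-screening, using the protocol's own six-month cut. Say how prayer is classed, since Section 2 lists it as a form of meditation.
4. Keep all controls in the pre/post contrast. Show any baseline or cross-sectional contrast by control practice status, without making a restricted control group the main analysis.

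The first option in step 1 costs one deleted clause; a separate cohort would need its own recruitment. The rest costs one or two screening questions and a small amount of extra analysis. If the questionnaires already ask about practice, only the classification rule is needed. With 5 to 20 controls, results by practice status will be imprecise and should be presented as descriptive.

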#### 6.3.2 Experiment B (Measuring the effects of meditation on the human organism)

Subject selection: Pre-event, registered participants [name] event will be contacted (i.e. email) and made aware of the research opportunity. Registered participants who are interested will be able to follow a link to a pre-screening questionnaire. Members of [name] meditation community who pass pre-screening qualify to participate. Depending on the event, we anticipate recruiting between 10 to 100 subjects.

Control Selection: In addition, we will identify controls by asking participants if they are traveling with family/friends who will be at the event but will not participate in the event; these may be volunteers of the event, and/or family/friends of meditators participating in the event. Controls will be age and sex matched to match subjects. We anticipate recruiting between 5 and 20 control subjects. The consenting as well as some baseline data (i.e. Medical history, demographics) collection will be performed electronically prior to the event.

Pre-event: Consenting: The consent form will be provided to the selected subjects for review prior to the event. The PI or designated research staff member will go over the consent form in person or via HIPAA compliant web meeting platform (i.e. Zoom). During this time, subjects will have ample time to have all questions and concerns addressed. We may also collect baseline

measures including physiological readouts (i.e. wearables, HRVs) and/or biological data (i.e. saliva).

Immediate Pre-event: Confirming of consent and baseline data (for those who did not use online option consenting and baseline data will be done). Vitals (i.e. height, weight, heartrate, temperature, blood pressure), physiological data (i.e. HRV, EEG, wearables), and biological data (i.e. saliva, blood) will be collected from all consented subjects and controls.

During event: Data collection during the event may include additional collection of questionnaire data, physiological data and biological data.

Immediate post-event: Vitals (i.e. height, weight, heartrate, temperature, blood pressure), physiological data (i.e. HRV, EEG, wearables), and biological data (i.e. saliva, blood) will be collected from all consented subjects and controls.

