# 8 Data Analysis

Demographic characteristics will be analyzed by descriptive statistics. Survey data are collected on an ordinal 4-point or 5-point Likert scale and treated as continuous variables during analysis. The data is then analyzed to describe the distribution. If the data is normally distributed, we will follow up with utilizing parametric statistics. However, if the data does not follow a classic normal distribution, we will utilize other methods such as reporting the median instead of the mean for central tendency and further analyze our results with frequencies, contingency tables, chi-square-tests, Spearman rho assessment, or the Mann-Whitney U test. All other questionnaires will be analyzed according to published protocols.

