## **10 Statistical Analysis**

Data analysis will be organized by Vitamed Research LLC. Vitamed Research LLC. staff has 10+ years of experience with statistical and data analysis. We will perform statistical analysis with appropriate parametric and non-parametric methods as described under Section 8.

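### The experience comparisons among meditators (Aim 2, and the novice-experienced part of Aim 3) have no age matching or adjustment; the protocol matches age and sex for controls only and names only unadjusted tests

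*Protocol*

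**What the plan says.** Section 2 sets Aim 2 as to "Evaluate and/or correlate brain waves (EEG) and physiological readouts (HRV, wearable data) of meditating subjects with their experience in meditation techniques". It divides the meditators into "novice (less than 6 months experience) and experienced meditators (more than 6 months experience" groups. Aim 3 compares molecular findings between novices, experienced meditators and controls.

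Section 4.2.1 admits meditators from age 18 with no upper limit. Section 6.3.2 expects 10 to 100 of them, depending on the event, and 5 to 20 controls. On balance it says only: "Controls will be age and sex matched to match subjects".

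Section 8 opens its account of methods with survey data: "Survey data are collected on an ordinal 4-point or 5-point Likert scale and treated as continuous variables during analysis". It continues: "If the data is normally distributed, we will follow up with utilizing parametric statistics". Otherwise it offers the median and "frequencies, contingency tables, chi-square-tests, Spearman rho assessment, or the Mann-Whitney U test". Section 10 extends this to the whole study: "We will perform statistical analysis with appropriate parametric and non-parametric methods as described under Section 8". Neither section names a covariate, a stratification or a regression model.

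Section 1 lists gender, age and body mass index among the parameters on which matching is possible at an event, and on that basis presents the study as closely controlled.

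**The concern.** People who have meditated for longer may also be older, and readouts such as HRV may change with age. If both hold, an age gradient shows up as an experience effect. Where the readout falls with age, it can hide or reverse a real benefit of experience; where it rises, it can create an apparent benefit.

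The protocol itself treats age as something to control, but the control it provides applies to a different contrast. Matching controls to meditators leaves the age distributions of novices and experienced meditators as they happen to fall. A correlation within the meditators does not use the controls at all.

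**Working it through.** The protocol gives no alpha, power, effect size or sample-size calculation, so there is no figure of its own to reproduce. The following shows how large the bias would be under stated assumptions.

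**Inputs**
- Number of meditators: 10 to 100 (Section 6.3.2); 50 is added as an intermediate value.
- Assumed: age-experience correlation 0.3 to 0.5.
- Assumed: age-readout correlation -0.3 to -0.5.
- Assumed: two-sided alpha 0.05.
- Assumed: no experience effect at fixed age.

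**Step 1: induced correlation.** With no association at fixed age, the marginal correlation is the product of the two:
- weak case: 0.3 × (-0.3) = -0.09
- strong case: 0.5 × (-0.5) = -0.25

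**Step 2: chance of a significant result.** By Fisher's z, let m = atanh(|r|) × √(n - 3). The chance is 1 - Φ(1.96 - m) + Φ(-1.96 - m). Here atanh(0.09) = 0.0902 and atanh(0.25) = 0.2554.

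| n | √(n - 3) | m, r = -0.09 | chance | m, r = -0.25 | chance |
|---|---|---|---|---|---|
| 10 | 2.646 | 0.239 | 5.7% | 0.676 | 10.4% |
| 50 | 6.856 | 0.619 | 9.5% | 1.751 | 41.7% |
| 100 | 9.849 | 0.889 | 14.4% | 2.516 | 71.1% |

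The nominal rate is 5%. The bias does not shrink as n grows, so the error rate rises with recruitment.

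**Step 3: simulation of the tests that Section 8 names, and of adjusted versions.** There were 3,000 runs per setting, over a wider range of assumed correlations and with an assumed 30% novices. False-positive rates at n = 100:

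| age-experience, age-readout | Spearman with length of experience | Mann-Whitney, novice vs experienced |
|---|---|---|
| 0.2, -0.2 | 7.9% | 5.7% |
| 0.4, -0.3 | 20.3% | 14.5% |
| 0.6, -0.5 | 81.5% | 59.3% |

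The two-group split is less affected than the correlation with length of experience. With age adjusted for (partial Spearman, or a group comparison with age as covariate), the rate was 4.4% to 5.7% in every setting at n = 10, 50 and 100.

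**The case against.** The strongest reply is that covariates are commonly left to a statistical analysis plan, which is not shown here, and that Section 10 promises appropriate methods. Unspecified parametric statistics could include regression. This stands in part: omitting a covariate list would not by itself be a finding. But Section 10 does not defer the choice. It points to Section 8, and every test named there is unadjusted. The protocol also uses age matching to support its claim of control and then provides it for one contrast only.

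A reader might infer that the protocol assigns Spearman or Mann-Whitney to Aim 2. It does not. They are options for non-normal data in a paragraph that starts from survey scales, and they reach Aim 2 only through the general reference in Section 10.

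A reader might also infer that age is ignored throughout, or that confounding by age is established. Neither is supported. Controls are age matched. Section 6.4.3 converts EEG to Z-scores against a normative database, which might absorb some of an age effect; the protocol does not say whether those norms depend on age, and it describes no such scoring for HRV or wearables. Section 6.4 says the QEEG is meant to describe change within each participant, and an age effect on the level of a readout may largely cancel in a change. Aim 2 does not say whether level or change is meant. No passage shows that age rises with experience, and an adult can begin at any age, so a cut at 6 months forces little age difference by itself.

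Finally, the work is exploratory, and at 10 subjects the excess error is small.

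**Conclusion.** The point holds in a limited form. As written, nothing balances or adjusts for age when meditators are compared by experience, and the named tests would not do so. Whether this distorts the results depends on correlations that the protocol does not give. Over the assumed range the consequence runs from slight (about 6% false positives at 10 subjects, weak case) to serious (about 71% at 100 subjects, strong case). The upper figure needs both correlations at 0.5 and recruitment at the stated maximum. The concern is strongest for correlations of HRV or wearable levels with length of experience. It is weaker for the 6-month split and may be weaker for within-person change and normative EEG scores. Because the aims are exploratory, this is an improvement that should be made, not a defect that invalidates the study.

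**What to change.** In Section 8, state that the experience analyses of Aims 2 and 3 use regression, or a partial rank correlation, adjusted for age and sex. Show the unadjusted result beside the adjusted one and label it an unadjusted association. At events with very few subjects, adjust for age alone or pool events.

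No new data are needed. Demographics are already collected, and age and sex are required in any case for matching the controls. The cost is one or two degrees of freedom and a change of wording.

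Body mass index and age bands need not be added. Height and weight are documented only among the Experiment B vitals, BMI might itself respond to sustained practice, and age bands are unworkable with about 10 subjects.
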